Duration of response is defined as the interval from the date of the first disease assessment indicating an overall response to the first documented relapse, disease progression, or death due to any cause, whichever occurs first. Subjects without relapse, disease progression or death until the analysis data cut-off date will be censored at the last adequate disease assessment date. Only subjects with a response will be evaluated for DOR.

DOR time in days = earlier of (date of first relapse or disease progression or death or date of censoring) – date of the first observation of overall response +1.

DOR time in months= earlier of (date of first relapse or disease progression or death or date of censoring) – (date of the first observation of overall response +1)/30.4

Overall Survival (OS)

Overall survival is defined as the time from enrollment until death due to any cause.

Subjects alive will be censored at the last known date. If the date last known to be alive is after the date that triggers the analysis (ie, the data cutoff date), the subject will be censored at the date of last contact through the analysis trigger date.

Event-free Survival:

Event-free survival (EFS) is defined as the interval from first administration of AMG 330 to the earliest of date of treatment failure, relapse for responders, or death due to any cause. Censoring is at the last evaluable post-baseline response assessment; otherwise,

at first administration of AMG330. For non-responders, the event date for treatment failure is assigned as the date of first administration of AMG 330.

Event-free Survival in days = earlier of (date of treatment failure or relapse or death or date of censoring) – date of the first administration of AMG 330 +1.

Event-free Survival in months = earlier of (date of treatment failure or relapse or death or date of censoring) – (date of the first administration of AMG 330 +1)/30.4.

Time to Response (TTR)

Time to response defined as the interval from the first administration of AMG 330 to the first documentation of response. Time to response is evaluated only for subjects who achieved a response.

Time to response is calculated as the number of days:

(date of first response – date of study day 1 +1).

6. Analysis Sets

The analysis of all endpoints, unless noted otherwise, will be conducted on the Safety analysis set defined in [Section 6.1](#).

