9.5.2 Analyses of Secondary Efficacy Endpoint(s)

The proportion of subjects with an overall response ([Section 5.4](#)) with corresponding exact 80% and 95% Confidence Intervals will be calculated using the Clopper-Pearson method ([Clopper and Pearson, 1934](#)) by cohort. The proportion of subjects who are event-free at 6 months with corresponding exact 80% CI will be calculated using the Clopper-Pearson method. The proportion of subjects with MRD response at the 0.1% threshold and the 0.01% threshold amongst subjects in the Safety Analysis Set will be summarized by cohort.

Listings indicating time to response, duration of response (DOR), and event-free survival will be produced for responders for each indication separately. For subjects in dose expansion cohorts, Kaplan Meier curves may be presented for event-free survival and overall survival with estimates for rates and 80% CI at selected weeks. DOR and time to response will only be analyzed for subjects who achieved an overall response.

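### SAP 5.4 censors event-free survival at day 1 for dosed, living subjects with no evaluable response assessment, while non-responders fail at day 1, so any Kaplan-Meier EFS curve is biased upward where such subjects occur

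*SAP*

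**What the plan says.** SAP 5.4 starts EFS at first dose: "Event-free survival (EFS) is defined as the interval from first administration of AMG 330 to the earliest of date of treatment failure", with relapse in responders and death from any cause as the other events. The censoring rule reads "Censoring is at the last evaluable post-baseline response assessment; otherwise", and the text continues "at first administration of AMG330. For non-responders, the event date for treatment failure is assigned as the date of first administration of AMG 330". The SAP defines neither non-responder nor treatment failure for EFS.

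SAP section 6 sets the population: "The analysis of all endpoints, unless noted otherwise, will be conducted on the Safety analysis set". SAP 6.1 defines that set as everyone enrolled who received at least one dose.

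SAP 9.5.2 uses EFS in two ways. The proportion event-free at 6 months is to be calculated with an exact 80% confidence interval. In addition, "For subjects in dose expansion cohorts, Kaplan Meier curves may be presented for event-free survival and overall survival", with estimates and 80% intervals at selected weeks. SAP 2.1 makes EFS a secondary endpoint for R/R AML and MDS, measured in the expansion cohorts only; MRD+ AML has relapse-free survival instead. SAP section 10 says EFS replaces time to progression in order to deal with subjects who are already progressing and never respond.

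**The concern.** Take a subject who is dosed, stops early, is alive and has no evaluable post-baseline assessment. In the response rate this subject is in the denominator and not in the numerator. In EFS the same subject has no recorded event and is censored at first dose. A subject known not to have responded is an event on that same day.

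All non-responders fail at day 1, so essentially only responders can be event-free afterwards, and EFS just after day 1 should equal the response rate. Censoring the unassessed instead treats them as exchangeable with the subjects still at risk, who are the responders. Early stopping for toxicity or decline is unlikely to be unrelated to outcome.

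Such subjects are foreseeable. In the 28-day schedule (Protocol Table 12) the day-8 marrow is optional and the first mandatory one is at day 29. Protocol 6.2.1.5 requires permanent discontinuation for some CRS events that can occur well before then. The end-of-treatment procedures in Protocol 7.2.3 include no marrow. What is at stake is whether EFS does the job for which SAP section 10 introduced it, which is to count those who never respond.

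**Working it through.** **Inputs.**
- Cohort size N = 30 and response rate 20%, so R = 6 (SAP 3.2). First stage: N = 10, R = 2 (SAP 3.2).
- U = subjects alive with no evaluable post-baseline assessment. The documents give no figure. Assumed range: 0 to 6 of 30 (0% to 20%).
- Time scale: difference in days plus 1 (SAP 5.4), so day-1 events and day-1 censorings are tied at t = 1.

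**Step 1: the plan's own figures.** The documents state no EFS value. The nearest figures are the exact 80% intervals for response. Clopper-Pearson gives 10.86% to 32.47% for 6/30 (half-width 10.81%) and 5.45% to 44.96% for 2/10 (half-width 19.75%). SAP 3.2 states 10.9% to 32.5% (10.8%) and 5.5% to 45.0% (19.8%), so both reproduce.

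**Step 2: Kaplan-Meier value just after day 1.** Day-1 events number N − R − U.
- Usual tie rule, events before censorings: S = 1 − (N − R − U)/N = (R + U)/N.
- Day-1 censorings removed first: S = 1 − (N − R − U)/(N − U) = R/(N − U).
- Unassessed counted as failures: S = 1 − (N − R)/N = R/N.

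For N = 30 and R = 6:

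| U | Events first, (6+U)/30 | Censorings first, 6/(30−U) | Unassessed as failures |
|---|---|---|---|
| 0 | 20.0% | 20.0% | 20.0% |
| 1 | 23.3% | 20.7% | 20.0% |
| 2 | 26.7% | 21.4% | 20.0% |
| 3 | 30.0% | 22.2% | 20.0% |
| 4 | 33.3% | 23.1% | 20.0% |
| 6 | 40.0% | 25.0% | 20.0% |

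For N = 10 and R = 2, U = 1 gives 30.0% (22.2% with censorings first), and U = 2 gives 40.0% (25.0%). A product-limit routine gave the same values. The direction is the same under either tie rule; the size is not.

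**Step 3: later times.** After day 1 only responders remain at risk, setting aside unassessed subjects who later die. Under the usual tie rule the curve is (R + U)/N times the responders' own curve, where the correct multiplier is R/N. The inflation factor is (R + U)/R, for example 9/6 = 1.5 at U = 3.

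Suppose U = 3 and 3 of the 6 responders relapse before 6 months. The Kaplan-Meier value at 6 months is 0.30 × 0.5 = 15.0%, against a correct 0.20 × 0.5 = 10.0%. The 15.0% is above the correct EFS and below the 20% response rate. In general the curve drops below the response rate once the responders' own curve falls below R/(R + U), here 6/9 = 67%.

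**Step 4: the 6-month proportion.** In the same example 3 responders are event-free at 6 months. Dividing by all dosed subjects gives 3/30 = 10.0%; leaving the 3 censored subjects out gives 3/27 = 11.1%. SAP 9.5.2 does not say which applies.

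**The case against.** The strongest reply is that SAP 5.4 says non-responders, not assessed non-responders. If the term means the same as in the response rate, an unassessed subject is a day-1 event, the event takes precedence over censoring, and there is no bias. The fallback clause would then serve subjects who have not reached a first assessment at a data cutoff, and SAP 7.1 does plan ad hoc analyses on unlocked snapshots. That use is legitimate, so it would be wrong to infer that the clause must be either biased or empty.

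The SAP does not state that restriction, however. Under SAP 7.1 and 7.2, formal interim analyses wait until all subjects concerned have ended study, and the primary analysis until each has 6 months on study or has terminated early. Almost nobody is still awaiting a first assessment then, so the clause as written reaches mainly those who left unassessed. The treatment-failure table in Protocol Appendix E includes wording on patients who do not complete the first course of therapy, but the EFS definition does not refer to it. Applied to R/R AML, it would conflict with the censoring clause.

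Other parts of the reply stand:
- U may be small. Protocol 6.2.1.5 asks for an end-of-infusion marrow when a shortened cycle is considered complete, and for every effort to perform the end-of-treatment and end-of-study visits. Protocol 7.2.4 includes a marrow at end of study. A recorded death is an EFS event.
- The Kaplan-Meier curves are optional and confined to the expansion cohorts.
- Protocol 10.4.3.2 treats efficacy analyses as exploratory, and the decision to extend an expansion cohort depends on response, not on EFS.

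**Conclusion.** The point holds on the plain reading of SAP 5.4. The rule handles the same unassessed subject differently in the response rate and in EFS, and any Kaplan-Meier EFS curve is biased upward wherever such subjects occur. At U = 3 of 30 the excess just after day 1 is 10.0 percentage points under the usual tie rule, close to the 10.8-point half-width the plan quotes for the response interval. It is 2.2 points if day-1 censorings are removed first.

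The size rests on an assumed U, on those subjects being alive with no evaluable assessment, and on the tie rule. Three stronger readings may suggest themselves and are not supported:
- That EFS lies above the response rate throughout. It lies above the correct EFS curve, but can fall below the response rate as responders relapse.
- That a doubling (40% against 20%) is to be expected. It needs 6 of 30 subjects alive and unassessed, and no document gives such a rate.
- That the 6-month event-free proportion is inflated too. The SAP leaves the handling of censored subjects unstated, so the fault there is a missing rule, not a demonstrated bias.

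**What to change.** In SAP 5.4, replace the fallback clause with text to this effect:
- Dosed subjects who discontinue or end study without an evaluable post-baseline response assessment are non-responders, with treatment failure on the date of first administration of AMG 330.
- Censoring at first administration is kept only for subjects still on study and awaiting their first response assessment at the data cutoff. Without this exception, a recently dosed subject would be failed in an ad hoc snapshot.
- Responders without relapse or death are censored at their last evaluable assessment.

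In SAP 9.5.2, apply the same rule to the proportion event-free at 6 months. For subjects no longer awaiting assessment, EFS just after day 1 then equals the response rate (6/30 = 20.0% in the example) whatever the value of U.

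The cost is a few sentences in the SAP, with no change to data collection. EFS may come out less favourable.

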6.1 Safety Analysis Set

Safety analysis set is defined as all subjects that are enrolled and receive at least 1 dose of AMG 330.

6.2 Dose Limiting Toxicity Evaluable Analysis Set

The DLT-evaluable Analysis Set includes all DLT-evaluable subjects. The analysis of DLT will be restricted to the DLT-evaluable Analysis Set. A subject is not DLT-evaluable if he/she drops out before completion of the DLT window for reasons other than an adverse event related to study drug or the subject has not received IP treatment for at least 14 days at the target dose for a 3- or 4-week cycle or at least 7 days at a target dose for a 2-week cycle. Furthermore, following drug interruptions, if a subject is unable to complete 2 repeat cycles for reasons other than DLT, the subject will not be DLT evaluable.

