### **Multiple Subject Cohorts (3+3 Dose Level Decision Rules)**

Based on nonclinical models, the dose for cohort 4 is predicted to be potentially efficacious. It is anticipated that up to 8 additional cohorts will be enrolled using a standard 3+3 design. Each cohort will enroll up to 6 evaluable subjects. There will be at least a 6-day (144-hour) interval between the start of treatment of the first and second subject in each cohort. On day 6 of this interval, the site investigator will evaluate all available safety and laboratory data for the treated subject and will send written confirmation on occurrence / non-occurrence of a DLT to the sponsor. The sponsor will only be able to open enrollment for the next subjects in the cohort after receipt of this confirmation. If deemed necessary, the 6-day interval may be extended until sufficient data are available to allow an assessment of the feasibility of treatment start of the next subject. The same guidance applies in case of intra-subject dose escalation, if applicable.

Following this, no more than 3 subjects should be enrolled into a cohort in two weeks.

Dose escalation decisions will be made in accordance with a standard 3+3 design using the rules noted in [Table 5](#).

- If no DLT is observed within the DLT window (see Section [6.2.1.4](#)) in the initial 3 subjects of a cohort, then dose escalation to the next higher dose level cohort will occur.
- If 1 DLT is observed within the DLT window in the initial 3 subjects of a cohort, then the cohort will be expanded to 6 subjects when 2 non-DLT subjects have reached the target dose. If no further DLT(s) are observed in the 6 subjects, then dose escalation to the next higher dose level cohort will occur. If  $\geq 2$  subjects experience a DLT in a cohort, then enrollment into this cohort will be stopped.
- See Section [3.4](#) for replacement of subjects

Dose escalation will occur at the planned dose levels until the MTD is determined or until the highest dose level is tested. The MTD is defined as the highest dose level with an observed incidence of DLT in  $< 33\%$  of subjects enrolled in a cohort dose level. At least 6 subjects will be treated at the MTD or highest tested dose.

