**Table 5. 3+3 Dose Level Decision Rules**

# Subjects a	#Subjects with DLT	Decision
3	1	Enroll 3 additional subjects at same dose level
3	0	Escalate b
3	≥ 2	De-escalate c
6	1	Escalate b
6	≥ 2	De-escalate c

[figure not shown]
a Subjects who are not DLT-evaluable (see Section 3.4) are excluded from the count of subjects

b If final dose level has been reached, accrual will be suspended.

c If 6 subjects already entered at next lower dose level, the estimated MTD has been established.

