### 3.1.3 Design of Group 3: MDS

The dose-escalation cohorts will estimate the MTD, safety, tolerability, PK, and PD of AMG 330 in subjects with MDS. The following dose escalation cohorts will be evaluated:

[REDACTED]

Selected

**target dose levels, with the exception of the maximal tested dose, that have been deemed safe in subjects with R/R AML (Group 1) could be skipped in Group 3 dose escalation cohorts based on available safety, PK, and PD data if recommended by the DLRT.** Administration of 8 mg IV dexamethasone within 1 hour prior to the dose step for prevention of cytokine release is mandatory. Up to 36 subjects with MDS will be enrolled in the phase 1a dose escalation cohorts; each dose escalation cohort will enroll a minimum of 3 and a maximum of 9 evaluable subjects.

### 3.1.4 Dose Escalation Rules for Groups 2 and 3

For both Group 2 and Group 3, a minimum of 3-4 subjects will be enrolled initially into each cohort and additional subjects up to a maximum of 9 evaluable subjects will be added at the Sponsor's discretion. After all subjects in each dose escalation cohort have either completed the DLT evaluation period or had a DLT, the DLRT will meet to determine whether it is appropriate to escalate or de-escalate the dose, or whether to stop the study for safety concerns. The DLRT will evaluate all available safety, laboratory, PK, and PD data to guide their dose-finding recommendations. **Based on DLRT recommendation, selected target dose levels, with the exception of the maximal tested dose, may be skipped in Groups 2 and 3 dose escalation cohorts if these dose levels have been evaluated in subjects with R/R AML (Group 1) and deemed safe.** [Appendix H](#) shows the mTPI-2 escalation/de-escalation guideline with a

target toxicity probability of 0.25 and an acceptable toxicity probability interval of 0.20 to 0.30. A dose level will be considered unsafe, with no additional subjects enrolled at that dose level, if it has an estimated  $> 95\%$  probability of exceeding the target DLT rate  $p_T$  (ie,  $P [DLT > p_T | \text{data}] > 95\%$ ) with at least 3 subjects treated and evaluated at that dose level. Dose exploration will continue until the current recommended dose cohort reaches at least 6 evaluable subjects or until the highest protocol-defined dose has been evaluated.

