### 3.4 Replacement of Subjects

Ineligible subjects (ie, subjects who were exposed to investigational product [IP] but post hoc were found to be ineligible) may be replaced. During dose escalation, subjects that are not DLT-evaluable will be replaced. A subject is not DLT-evaluable if he/she drops out of cycle 1 before completion of the DLT window for reasons other than an adverse event related to study drug **or the subject has not received IP treatment for at least 14 days at the target dose for a 3- or 4-week cycle or at least 7 days at a target dose for a 2-week cycle**. Following drug interruptions, if a subject is unable to

complete 2 repeat cycles for reasons other than DLT, the subject will not be DLT evaluable and can be replaced. All available safety data for subjects who are not DLT evaluable will still be evaluated and considered in DLRM decisions. No dose escalation will occur unless at least 3 subjects have **been assessed as DLT evaluable**.

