### DLT Evaluation

A subject is not DLT-evaluable if he/she drops out before completion of the DLT window for reasons other than an adverse event related to study drug **or the subject has not received IP treatment for at least 14 days at the target dose for a 3- or 4-week cycle or at least 7 days at a target dose for a 2-week cycle**. All available safety data for subjects who are not DLT evaluable will still be evaluated and considered in DLRM decisions. No dose escalation will occur unless at least 3 subjects have **been assessed as DLT evaluable**. Duration of a cycle might be extended and be different from the duration of the DLT window. For all cohorts, the DLT window may also be extended

retrospectively to assess events starting or persisting outside the window in case the DLT definition is time dependent (eg, in case of neutropenia, see below).

Any adverse event occurring outside the DLT window that is determined by the investigator to be possibly related to the investigational product, which is seen more frequently or is more severe than expected or is persistent despite appropriate management, can be determined to be a DLT upon unanimous decision by the DLRT after review of the adverse event and all available safety data.

Events listed below are to be considered as DLTs and exceptions when occurring in a subject during the DLT window unless clearly attributable to causes other than AMG 330 treatment:

- Any treatment-related death.
- Grade 4 neutropenia lasting  $\geq$  42 days from start of cycle in absence of evidence of active AML (in case of 3 or 4 weeks treatment cycles, the number of days would increase accordingly)
- Grade 3–5 non-hematologic toxicity not clearly resulting from the underlying leukemia EXCEPT:
  - Alopecia
  - Grade 3 fatigue, asthenia, fever, anorexia, or constipation
  - Grade 3 nausea, vomiting or diarrhea not requiring tube feeding, total parenteral nutrition, or requiring or prolonging hospitalization
  - Infection, bleeding, or other expected direct complication of cytopenias due to active underlying leukemia
  - Grade 3 infusion reaction, if successfully managed and which resolves within 72 hours
  - Grade 3 rash
  - Grade 3 or 4 tumor lysis syndrome if it is successfully managed clinically and resolves within 7 days without end-organ damage.

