Dexamethasone (8 mg IV) should be administered within 1 hour prior to restart and within 1 hour prior to the dose step(s). The subject should be hospitalized starting from restart of infusion until 72 hours after the dose step. After the dose step, assessments of vital signs, pulse oximetry and clinical evaluation should be performed as per the schedule of assessments for dose steps ([Table 14](#)).

The number of days of infusion at the target dose before and after an interruption should sum up to the planned duration, ie, minimum 10 days at the target dose for a 14 day

cycle, and minimum 14 days at the target dose for a 21 or 28 day cycle. In this case, the subject would still be DLT-evaluable. However, if the cycle was interrupted for more than 7 days, a new cycle should be started and the interrupted cycle would not be evaluable for DLT, unless the event that lead to the interruption was a DLT.

Please refer to the table below to determine the minimum duration of treatment for a subject to be counted as DLT evaluable.

**Note:** In case a treatment cycle is considered complete but lasted less than the planned number of days (14, 21, or 28, as applicable), the EOI bone marrow assessment should be performed once it was confirmed that the cycle will not be resumed in order to assess treatment response and determine the infusion-free interval prior to start of the next cycle, if applicable. Bone marrow and blood samples (for [REDACTED], immune cells, and plasma biomarker testing) should also be sent to the applicable central laboratories.

Planned Treatment Duration	Minimum Duration of Treatment at Target Dose to be Counted as DLT evaluable
2 weeks	7 days at target dose
3 weeks	14 days at target dose
4 weeks	14 days at target dose

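### The minimum-exposure ground for being not DLT-evaluable has no exception for a subject who had a DLT, so as written it removes early DLTs from the DLT summary and the final MTD/RP2D estimate

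*SAP*

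**What the plan says.** SAP 6.2 gives three grounds for being not DLT-evaluable. The first is dropping out before the DLT window ends for a reason other than a drug-related adverse event. The second is too little exposure: "or the subject has not received IP treatment for at least 14 days at the target dose for a 3- or 4-week cycle", or fewer than 7 days for a 2-week cycle. The third is failing to complete two repeat cycles for reasons other than a DLT. The first and third carry an exception; the second does not. Protocol 3.4 has the same three grounds. Protocol 6.2.1.4 (DLT Evaluation) has the first two, again with an unqualified "or the subject has not received IP treatment for at least 14 days at the target dose". The minimum-duration table in Protocol 6.2.1.5, introduced by "Please refer to the table below to determine the minimum duration of treatment for a subject to be counted as DLT evaluable", repeats the minimum without an exception.

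Elsewhere the protocol keeps subjects with a DLT:

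- Protocol 6.2.1.5, on a cycle interrupted for more than 7 days: "the interrupted cycle would not be evaluable for DLT, unless the event that lead to the interruption was a DLT".
- Protocol 6.2.1.5, below Table 6: two unsuccessful restarts make a subject non-evaluable only where no DLT was seen.
- Protocol 3.1.1, by implication: after 1 DLT in 3, "then the cohort will be expanded to 6 subjects when 2 non-DLT subjects have reached the target dose".
- Protocol 3.1.4, by implication: the dose review takes place "After all subjects in each dose escalation cohort have either completed the DLT evaluation period or had a DLT".

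The evaluable set drives several outputs. Table 5 footnote a states "Subjects who are not DLT-evaluable (see Section 3.4) are excluded from the count of subjects". Protocol 10.1.2 and SAP 9.6.2 restrict the DLT analysis to it. Protocol 3.1.5 and SAP 3.1 base the final MTD/RP2D estimate on it. Protocol 3.4 adds: "During dose escalation, subjects that are not DLT-evaluable will be replaced".

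**The concern.** Under Protocol 6.2.1.5 a DLT is a reason for immediate interruption and, except where there is clear clinical benefit, for permanent discontinuation. A subject whose DLT falls in the run-in, at a dose step or early at the target dose will therefore usually miss the 14-day or 7-day minimum. One type always does so in cycle 1 of a step-dosed cohort: once the initial-dose MTD is defined, grade 3 CRS at that dose is a DLT (Protocol 6.2.1.4) and ends treatment (Table 7), before any day at target dose.

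Subjects would then leave the DLT set because of the outcome the set exists to measure, and during escalation they would be replaced. The resulting bias in the DLT rate can only be downward. DLT incidence is part of the primary endpoint and MTD estimation is a primary objective.

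**Working it through.** **Plan's own figures first.** SAP 3.2 gives the chance of at least one DLT for true rates of 10–33%. With 3 subjects: 1 − 0.90³ = 27.1% and 1 − 0.67³ = 69.9%. With 6: 1 − 0.90⁶ = 46.9% and 1 − 0.67⁶ = 91.0%. These match the stated 27–70% and 47–91%, and they hold only if every DLT is counted.

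**Inputs.** p is the true DLT rate, q = 1 − p, and f is the share of DLT subjects below the exposure minimum. The documents do not give f; 25% and 50% are assumptions. Rules are applied mechanically, and subjects without a DLT meet the minimum or are replaced independently of outcome.

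**Rate in the evaluable set.** r = p(1 − f)/(1 − pf). At p = 33%:

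- f = 25%: 0.2475/0.9175 = 27.0%
- f = 50%: 0.165/0.835 = 19.8%

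The 3-subject detection chance, 69.9% at f = 0, becomes 1 − (1 − r)³ = 61.1% or 48.3%.

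**Chance that a Group 1 3+3 cohort escalates.** With every DLT counted it is q³ + 3pq⁵; at 33%, 0.301 + 0.134 = 0.434. With the clause in force, the answer depends on which text governs:

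- *A. The stop rule counts every DLT in the cohort and footnote a governs only the count of subjects.* P = q³ + 3pf·q³ + 3p(1 − f)q⁵. The middle term is a dropped DLT followed by a DLT-free replacement. At 33%: f = 25% gives 0.301 + 0.074 + 0.100 = 0.475; f = 50% gives 0.301 + 0.149 + 0.067 = 0.516.
- *B. Footnote a governs throughout.* P = (1 − r)³ + 3r(1 − r)⁵. At 33%: 0.557 or 0.714.
- *C. The body text of Protocol 3.1.1 governs and the DLT subject is counted.* No change.

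| True DLT rate | Evaluable-set rate, f = 25% / 50% | Escalate, f = 0 (and C) | Escalate, A, f = 25% / 50% | Escalate, B, f = 25% / 50% |
|---|---|---|---|---|
| 10% | 7.7% / 5.3% | 91% | 92% / 93% | 94% / 97% |
| 25% | 20.0% / 14.3% | 60% | 63% / 67% | 71% / 83% |
| 33% | 27.0% / 19.8% | 43% | 48% / 52% | 56% / 71% |

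**Illustration for Groups 2 and 3.** Take 6 subjects, 2 with a DLT, one of those two below the minimum. Counted, this is 2/6 (33%), which the SAP 3.3 monitoring table reads as de-escalate. If that subject is dropped and replaced by one without a DLT, it is 1/6 (17%), which the table reads as escalate. The case is constructed to show the mechanism, not its frequency.

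**The case against.** The strongest reply is that the intent is clear. Both relevant sentences of Protocol 6.2.1.5, the repeat-cycle ground in SAP 6.2, and the cohort rules in Protocol 3.1.1 and 3.1.4 all keep a subject with a DLT. The exposure ground would also nearly empty the drug-related exception in the drop-out ground, because many subjects leaving for such an event will be below the minimum. The exception in Protocol 6.2.1.5 addresses a different trigger, an interruption of more than 7 days, and meets the exposure ground only when the DLT subject is also under-exposed. All of this stands. It shows an omission rather than a chosen rule, but a programmer working from SAP 6.2 would still exclude these subjects.

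The second reply is that live decisions do not rest on the set alone. Protocol 3.4 and 6.2.1.4 require safety data from non-evaluable subjects to be considered at dose reviews. Protocol 10.3.1 and SAP 7.1 bring in DLTs from all subjects. The Group 1 MTD definition and stop rule refer to subjects in the cohort, and the expansion-phase suspension trigger refers to subjects treated. The events also remain in the adverse event tables on the Safety Analysis Set. This stands as well. A reader might infer from column B that the plan would routinely escalate past toxic doses. The documents do not support that: B requires footnote a to override the stop rule, f is unknown, and the review team sees every DLT.

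**Conclusion.** The definition is wrong as written and should be fixed. The missing exception and its inconsistency with Protocol 6.2.1.5 are matters of text and do not depend on any assumption. The outputs most exposed are the programmed DLT summary and the final MTD/RP2D estimate, which are confined to evaluable subjects and lack the safeguards that protect escalation decisions.

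The direction of the bias is downward. Its size is conditional. At a true rate of 33%, f of 25% or 50% lowers the evaluable-set rate by 6.0 or 13.2 percentage points, and at f = 0 nothing changes. The 3+3 escalation chance of 43% moves to 48% or 52% if the stop rule counts every DLT, to 56% or 71% only if footnote a governs throughout, and not at all if the DLT subject is counted.

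A reader might also infer that every event called a DLT should make its subject evaluable. The documents do not support that. Protocol 6.2.1.4 lets the review team declare DLTs outside the window, whereas the 3+3 and suspension rules count events within it. Admitting under-exposed subjects only because of a late event would be outcome-dependent selection in the other direction. Protocol 3.1.1 also keeps DLTs after intra-subject escalation out of 3+3 decisions.

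**What to change.** Add one sentence to SAP 6.2, Protocol 3.4, Protocol 6.2.1.4 and the minimum-duration table in Protocol 6.2.1.5:

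*A subject with a DLT within the DLT window (including any extension under Protocol Section 6.2.1.4) is DLT-evaluable regardless of days at target dose; the minimum-exposure requirement applies only to subjects without such a DLT.*

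List DLTs declared by the review team outside the window separately, and leave DLTs after intra-subject escalation outside the 3+3 count, as Protocol 3.1.1 states.

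Three related points need settling with it:

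- State to which MTD a DLT before the target dose is attributed, since Protocol 3.1.1 estimates one for each dose step and one for the target dose.
- Reconcile the minimum for a 14-day cycle in Protocol 6.2.1.5, where the text says 10 days at target dose and the table says 7.
- Reconcile the Group 1 denominators: subjects enrolled (Protocol 3.1.1 and 6.2.1.4, SAP 7.1) against DLT-evaluable subjects (Table 5, Protocol 3.1.5, SAP 3.1).

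The cost is wording only, with no new data or subjects. The downside for the sponsor is that reported DLT rates may be less favourable.
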